#### Duration of Therapy

Patients will remain on Omegaven™ until weaned from PN. Patients may continue monotherapy with Omegaven™ as an additional source of calories after the dextrose/protein portion of PN is discontinued

In the event that a patient who has been listed for a liver or liver/intestinal transplant has an organ become available, the participation in this protocol will not preclude them from receiving the transplant.

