#### Discontinuation of Therapy

Patients will continue to be followed by the PI if in-patient or if discharged they will be followed in the Out-Patient GI Clinic upon discontinuation of therapy with Omegaven™ for a minimum of 2 months after the treatment is stopped.

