## **9.0 Study Withdrawal/Discontinuation**

Patients will be withdrawn from the study for any of the following:

- a) Toxicity considered unacceptable by the Principal Investigator
- b) Patient/guardian requests to discontinue treatment and/or observation for any reason.
- c) A suitable organ has been located and the patient is able to undergo a liver or liver/intestinal transplant.
- d) Decision by the Principal Investigator that termination is in the patient's best medical interest.

In the event that a patient is withdrawn from the protocol, study staff will document the date of withdrawal, the reason for withdrawal, and the results of all measurements of interest made up to date of withdrawal.

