### ***Analysis of Efficacy of Omegaven™***

The primary outcome to gain preliminary evidence of efficacy will be based on the time from baseline to normalization of bilirubin level, i.e, first time point among three consecutive in which bilirubin is  $< 2\text{ mg/dL}$ . We do not anticipate that any subject will present a rebound on direct bilirubin after normalization. However, we will describe the cohort with respect to the frequency of rebounds in bilirubin levels.

Crude comparisons of time to normalize direct bilirubin levels using Omegaven™ Results of these analysis will be compared with results of analysis excluding subjects who die or are transplanted. Time to reach a total bilirubin of 1.2 will also be compared using survival analysis methods. Analysis of this outcome will proceed as described for direct bilirubin.

We will also describe individual profiles over time (i.e., 2 months before baseline or birth until end of follow-up period) for all subjects using graphical methods. Trends in liver function markers over time will be explored using generalized linear models in which correlations of observations within subjects will be accounted using a generalized equations or random effects approach. In these models we will hypothesize that for both groups biochemical levels increase for all tests with equal slope before treatment. After treatment, however, levels should be decreasing for patients in the Omegaven™ group. We will perform these analyses including only subjects who did not die or undergo transplantation and including all subjects but assigning for subjects who died or underwent a transplant their worse possible outcome after they died or had the transplant. Using descriptive statistics, we will also explore the association between spikes in blood tests over time and predictors including transfusions of red blood cell products and blood stream infections.

Assessment of efficacy will be also based on comparison of means (or medians) of the mean and maximum modified PELD scores of each subject across all follow-up weeks. Adjustments of these comparisons for potential confounders will be based on linear regression models. Mean rates of infection will be compared. Liver transplant, mortality, and red blood cell product transfusion events will be collected.

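### The supportive PELD comparison uses each infant's mean and maximum score over open-ended follow-up, so it is confounded with entry severity and, mainly for the maximum, with weeks observed

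*Combined protocol and SAP*

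**What the plan says.** The efficacy part of section 10.0 makes time to bilirubin normalization the primary efficacy outcome. It then adds a PELD assessment, which compares, by mean or median, "the mean and maximum modified PELD scores of each subject across all follow-up weeks". On covariates it says only: "Adjustments of these comparisons for potential confounders will be based on linear regression models". Neither baseline PELD nor length of follow-up is named.

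Four other provisions fix how many weeks an infant contributes:

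- Section 6.0, Duration of Therapy: "Patients will remain on Omegaven™ until weaned from PN".
- Section 6.0, Discontinuation of Therapy: follow-up then continues "for a minimum of 2 months after the treatment is stopped", with no upper limit and no common end date.
- Section 9.0 ends participation for unacceptable toxicity, at the family's request, when "A suitable organ has been located and the patient is able to undergo a liver or liver/intestinal transplant", or on a "Decision by the Principal Investigator that termination is in the patient's best medical interest".
- Section 9.0 also says that what is documented for a withdrawn infant is "the results of all measurements of interest made up to date of withdrawal".

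For the trend models of liver markers, section 10.0 plans two analyses of death and transplant. One leaves those infants out; the other assigns them the worst outcome from the event onward. That text comes before PELD is introduced and is not extended to it. Sections 2.0 and 5.0 describe the study as non-randomized.

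**The concern.** A summary over all follow-up weeks is comparable between infants only if the weeks are comparable. Here they run from entry to an end that depends on weaning, on later clinic follow-up, and sometimes on the outcome itself.

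Three problems follow. A per-infant maximum can only stay level or rise as more weeks are added. A mean over a course that trends depends on where the course is cut. Neither summary refers to the infant's starting score, and in a non-randomized comparison nothing in the design balances that score. Entry needs direct bilirubin above 2.5 mg/dL, with no upper limit and no PELD range.

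At stake is whether a PELD difference between the Omegaven and soybean groups can be read as a treatment effect. As written, it could partly reflect who entered sicker and who was observed longer.

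**Working it through.** The documents state no PELD mean, SD, week-to-week correlation, follow-up distribution, sample size or alpha. There is no figure to reproduce, and every value below except the minimum follow-up rests on assumptions.

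**1. Maximum, no true change.** Weekly scores are a stable level plus noise of SD 1, with first-order autocorrelation rho (100,000 simulated series). Expected maximum above the infant's own level, in SD:

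| rho | 4 weeks | 12 weeks | 26 weeks | 26 minus 12 | 26 minus 4 |
|---|---|---|---|---|---|
| 0 | 1.03 | 1.63 | 1.98 | 0.35 | 0.95 |
| 0.5 | 0.82 | 1.47 | 1.86 | 0.39 | 1.04 |
| 0.8 | 0.55 | 1.13 | 1.57 | 0.44 | 1.02 |

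**2. Which contrast is relevant.** Section 4.0 expects at least 30 more days of PN at entry, and section 6.0 adds at least 2 months (about 61 days). That makes (30 + 61)/7 = 13 weeks for an infant who meets that expectation and is neither withdrawn, transplanted nor lost to death. So 12 against 26 weeks is the more typical comparison, and 4 weeks applies mainly to early death, transplant or withdrawal.

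**3. Mean, no true change.** With true score 15 and within-infant SD 4, the expected mean stays at 15.0 from 4 to 52 weeks. Length alone does not bias the mean.

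**4. Mean, with a trend.** The expected mean over weeks 0 to w of a straight course is start + slope × w/2.

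- Improving from 20 at 0.5 per week: 20 − 0.5 × 2 = 19.0 at 4 weeks, 20 − 0.5 × 6 = 17.0 at 12, and 20 − 0.5 × 13 = 13.5 at 26.
- Worsening from 20 at 0.5 per week: 20 + 0.5 × 2 = 21.0 if cut at week 4, against 20 + 0.5 × 13 = 26.5 at week 26. With SD 4 and rho 0.5, the simulated maxima are 24.9 and 36.8. The infant lost early looks better on both summaries.

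**5. Entry severity.** Same 12-week window, SD 4, rho 0.5. An infant entering at 25 and improving by 0.5 per week has mean 22.0 and maximum 28.8. One entering at 15 and worsening by 0.3 per week has 16.8 and 23.1. In a mixed population (entry mean 15, SD 5; slope mean −0.2, SD 0.2; 4 to 39 weeks; independent weekly noise of SD 4), both summaries correlate 0.87 with entry score. The mean correlates 0.37 with slope and the maximum 0.24.

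**6. False-positive rate.** 20 infants per group, between-infant SD 5, within-infant SD 4, rho 0.5, no change and no treatment effect, two-sided t-test at 0.05 (4,000 repetitions):

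| Follow-up, group 1 vs 2 | Mean | Maximum | Change at week 8 |
|---|---|---|---|
| 12 vs 12 weeks | 5.3% | 5.4% | 5.0% |
| 8 vs 26 weeks | 5.3% | 25% | 4.9% |
| 8 vs 52 weeks | 5.2% | 51% | 4.6% |

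The last two rows assume that a whole group is followed for less time than the other. The documents do not show this. The rows indicate how the maximum behaves if it happens.

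**The case against.** A reader might infer that these summaries measure time on study and entry severity instead of improvement, or that the maximum cannot show benefit. The documents and the arithmetic do not support that. With equal entry at 20 and an equal 12-week window, slopes of 0, −0.5 and −1 per week give means of 20.0, 17.0 and 14.0 and maxima of 26.1, 23.7 and 22.5. Both summaries respond to improvement, the maximum less so. Aim 2 includes halting progression as well as reversing disease. Against a comparator that keeps worsening, the maximum can separate the groups: over 26 weeks from 20, the improving course has an expected maximum of 23.8 and the worsening one 36.8.

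Other points on that side also stand:

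- PELD is an additional assessment in a study of preliminary efficacy, and individual profiles and trend models of liver markers are planned as well.
- Regression adjustment is planned. Entry severity is an obvious candidate covariate, so that part is underspecified, not absent.
- Weaning does not itself end follow-up.
- Hypothesis 2.4 concerns transplant, hepatic death and transfusion. Section 10.0 collects transplant, mortality and red cell transfusion events separately, so the weakness should not be charged to that hypothesis.
- No imbalance in follow-up between the groups has been shown.

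This lowers the weight of the point but does not remove it. Naming baseline PELD as a covariate would address entry severity. It would not equalize the windows or deal with courses cut short by death or transplant. The trend models cover liver markers and do not repair the PELD comparison.

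**Conclusion.** The concern holds in a limited form. The PELD comparison is confounded with entry severity and, especially for the maximum, with weeks observed. The mean is affected only when scores trend or when the end of follow-up is related to outcome. In that case early death or transplant can flatter a deteriorating infant.

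The size cannot be derived from the documents. Under a stable course, the maximum gains about 0.35 to 0.44 within-infant SD between 12 and 26 weeks, for correlations of 0 to 0.8. The gain of about 1 SD from 4 to 26 weeks should not be presented as typical, for the reason in step 2 of the working. A false group difference in the maximum also requires follow-up to differ between the groups; the documents neither show that it does nor include anything to prevent it.

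Because PELD is supportive, the plan should be amended here, but the primary outcome does not depend on it.

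**What to change.** Replace the PELD sentence in section 10.0 with a specification along these lines:

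- Compare modified PELD between groups at fixed times in one common window, for example weeks 4, 8 and 12 from a baseline dated in the same way in both groups.
- Adjust for baseline PELD in the linear regression already planned, and name any other covariates.
- Define visit windows. The footnote to Table 3 allows less frequent testing in stable, improved infants, so a score may not exist at every week.
- Apply to PELD the two death and transplant analyses already stated for the trend models (exclusion, and worst outcome assigned). State the assigned value in advance and report the number of infants affected in each group.
- Report the maximum descriptively only, within the same window.

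The main cost is drafting. Scores after the window would be described but not used in the comparison, and infants without a score in a visit window contribute less.

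Two things need checking first, because the available text does not settle them. One is the definition of modified PELD, which determines the tests required. The other is the soybean group's testing schedule, since Tables 2 and 3 are written for Omegaven therapy.

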#### **Limitation of Study**

Biases in our efficacy estimates could also result from misclassification, since the marker of reversal of cholestasis, i.e., direct bilirubin does not accurately translate all components of liver function.

### **11.0 Privacy/Confidentiality Issues**

Study data will be collected on paper Case Report Forms (CRF's) developed by the PI. The CRF can only be accessed by valid investigators in the study. Study participants are only identified in the CRF with a sequentially generated study number. A paper Log with the identifiers of the study subjects will be kept in a locked research office and only available for view to the PI, Sub-Investigators, the safety monitor if requested and the FDA if requested.

Infants and children enrolled will be assigned a study number that will identify the patient on Case Report Forms. Study numbers will be assigned sequentially with enrollment. Only the investigators involved with the study will have access to the log revealing which patients were assigned which study

numbers. No identifiable information (such as patient name, medical record number) is included in the CRF.

## **12.0 Follow-up and Record Retention**

The original copy of the electronic CRF will remain on server for six years after the conclusion of the trial, and then destroyed.
